2 SYNOPSIS

Title of Study	A Drug Utilization Study on the Real-world Usage of Levonorgestrel 20microgram/24 Hours Intrauterine Delivery System
Protocol Number	7037167
Selected Countries	Czech Republic, Poland, Serbia, Slovakia
Background and Rationale	Levosert®is a levonorgestrel (LNG)-releasing intrauterine system (IUS) containing 52 mg of levonorgestrel. In Europe, Levosert is indicated for use in 1) contraception and 2) menorrhagia or heavy menstrual bleeding.
	Levosert was first authorised in Europe via Decentralised Procedure (DCP; licence number UK/H/3030/001/DC) on 28 Dec 2012 for the treatment of heavy menstrual bleeding for three years. Countries targeted for the proposed study (Czech Republic, Poland, Serbia, and Slovakia) authorized Levosert for the treatment of heavy menstrual bleeding in a separate DCP (HU/H/0580/001/DC) in 2013. In 2014, the second indication 'contraception' was approved with new supportive data from the ongoing pivotal Phase 3 study M360-L102. Since then and based on the results of the same Phase 3 study, the duration of use of Levosert® for use in contraception was extended to 5 years, then to 6 years in all European countries where the product is marketed. However, the ongoing Study M360-L102 was designed to evaluate contraceptive efficacy only (not heavy menstrual bleeding), and thus, there is need for further evidence regarding usage for the menorrhagia indication to support its use up to the recommended duration determined for the contraception indication. In the context of a lack of data to support extension of recommended duration of use for
	menorrhagia indication, the Sponsor has committed to the Danish Medicines Agency to conduct a drug utilisation study (DUS) concerning the real-world usability of Levosert 20 microgram/24 hours Intrauterine Delivery System in the menorrhagia indication.
Objectives	The primary objective is to describe the duration of Levosert utilization for the indications of contraception and heavy menstrual bleeding (with and without intended contraception) amongst prescribing OB-GYNs in the selected countries.
	The secondary objective is to characterize IUS prescribing practices, utilization patterns of Levosert, and level of satisfaction with Levosert for both indications.
Study Design	This is a cross-sectional study collecting data from OB-GYNs who prescribe Levosert in four (4) European countries: Czech Republic, Poland, Serbia, and Slovakia.
	The questionnaire will collect quantitative data by means of closed-ended questions. Responding to the questionnaire is expected to take not more than twenty (20) minutes. Prescribers will be asked to report about all the patients they have managed with Levosert, including numbers of Levosert prescriptions and removals (with or without replacements). Individual patient date will not be reported. Instead, data will be considered aggregate and will be fully anonymous.
	The estimated duration of the study (from programming the survey to statistical analysis and report writing) is approximately 1 year.

13-02-2023 This document is confidential.

Selection of Survey Population (Prescribers)

Inclusion criteria:

- HCP has its primary practice located in Czech Republic, Poland, Serbia, and Slovakia
- HCP's primary state-certified medical specialty is Gynaecology and Obstetrics.
- HCP spends at least 25% of their professional time in direct patient care, as opposed to teaching, research, or administrative roles
- HCP has prescribed Levosert for HMB to at least two (2) patients
- HCP has removed or replaced Levosert from at least one (1) patient who received the product for HMB

Exclusion criteria:

- HCP is not a physician
- HCP never prescribed Levosert
- HCP or any member of the HCP's household is affiliated with or employed by any
 pharmaceutical companies as a consultant and/or researcher (other than participating in
 clinical studies or clinical investigations)

Data Management and Quality Control

The survey will be fielded through an online survey platform tool and data will be collected on a real-time basis and will be stored in a cloud-based environment.

The collection of personal data of participating Prescribers will be limited to the amount necessary to achieve the aims of the research and for respondent compensation. No patient-level data (e.g., from healthcare records) will be collected. De-identified data will be sent to the Study Coordinating Centre for statistical analysis.

Data will only be collected in electronic form and no hard copy documents will be retained.

The Study Coordinating Centre will be responsible for data quality, ensure that the study is conducted in accordance with the protocol and monitor data accrual on an ongoing basis.

Sample Size and Statistical Analysis

Based on expected availability of OB-GYN respondents in a large physician panel, a convenience sampling approach is applied with a target sample size of 380 physicians who collectively are estimated to have removed approximately 820 Levosert IUS across both indications.

Primary endpoint: Expected usage duration of Levosert for both indications, defined as the difference in time between removal (with or without replacement) and insertion of the device.

Secondary endpoints: Number of IUS prescriptions, number of Levosert prescriptions and removals (with or without replacement), distribution of patients by type of contraception, distribution of patients using IUSs who are receiving Levosert, distribution of patients receiving Levosert for heavy menstrual bleeding who show treatment effectiveness by the end of each year, distribution of patients getting Levosert removed by the end of each year, and level of satisfaction with Levosert.

All analyses will be descriptive (total, by country, by indication). Categorical variables will be summarized using counts and percentages. Continuous variables will be summarized using the number of observations (n), mean, standard deviation (SD), median, minimum, and maximum, interquartile ranges (IQR), and 95% confidence intervals (CI), as appropriate.

Ethical and Regulatory Obligations	The study will be approved by an appropriately constituted Ethics Committee in Czech Republic, Poland, Serbia, and Slovakia. Approval is required for the study protocol, any potential protocol amendments, recruitment material (i.e., screener) and participant facing material (i.e., questionnaire) before any Prescriber can be enrolled. All applicable laws and regulations will be followed within the countries in which the survey is performed.
Sponsor	Gedeon Richter
Study Coordinating Centre	Syneos Health

13-02-2023

3 T	ABLE OF CONTENTS	
1 (GENERAL INFORMATION	4
2 8	SYNOPSIS	
3 1	ΓABLE OF CONTENTS	5
	of Tables	
	of Figures	
4 I	LIST OF ABBREVIATIONS	11
5 F	BACKGROUND AND RATIONALE	12
5.1	Background	
5.2	Rationale	
6 (OBJECTIVES	13
6.1	Primary Objective	
6.2	Secondary Objectives	
7 N	METHODOLOGY	13
7.1	Discussion of Study Design	13
7.2	Survey Population	12
8 8	SELECTION OF SURVEY POPULATION	15
8.1	Prescriber Eligibility Criteria	15
8.1	1.1 Inclusion Criteria	15
8.1	1.2 Exclusion Criteria	15
8.2	Randomization	15
8.3	Risk and Benefit	15
8.4	Study Withdrawal, Removal, and Replacement of Prescribers	15
9 I	DATA MANAGEMENT AND QUALITY CONTROL	

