10.3 Data Analysis

All analyses will be descriptive in nature. Categorical variables will be summarized using counts and percentages. Continuous variables will be summarized using the number of observations (n), mean, standard deviation (SD), median, minimum, and maximum, interquartile ranges (IQR), and 95% confidence intervals (CI), as appropriate. In addition, utilization patterns of Levosert will be visualized using plots or similar techniques.

1. Geographical distribution of Prescribers (by country)

- 2. Count and percentage of Prescribers by ranges of their professional time spent on direct patient care
- 3. Count and percentage of Prescribers by duration of their medical practice
- 4. Count and percentage of Prescribers by practice setting
- 5. Count and percentage of Prescribers having prescribed each brand of levonorgestrel IUS
- 6. Count and percentage of Prescribers having experience removing each brand of levonorgestrel (with or without replacement)
- 7. Descriptive statistics on Prescribers' count of IUS prescriptions in the past 10 years
- 8. Descriptive statistics on Prescribers' count of Levosert prescriptions and removals (with or without replacement), by indication
- 9. Descriptive statistics on Prescribers' count of patients they personally manage in a typical month without COVID-19 restrictions
- 10. Descriptive statistics on percentage of Prescribers' patients by type of contraception, by indication
- 11. Descriptive statistics on percentage of Prescribers' patients using IUSs who are receiving Levosert, by indication
- 12. Distribution of Prescriber's patients at the time of Levosert prescription among age categories, by indication
- 13. Count and percentage of Prescribers among categories of duration-of-effectiveness of Levosert for heavy menstrual bleeding
- 14. Percentage of Prescribers' patients getting Levosert removed by the end of each year, by indication
- 15. Descriptive statistics on the total duration of use of Levosert in patients who use Levosert for more than six years, by indication
- 16. Percentage of Prescribers' patients who use Levosert for heavy menstrual bleeding indication who would continue to show treatment effectiveness by the end of each year
- 17. Distribution of Prescribers' patients among reason-for-removal categories, by indication
- 18. Count and percentage of Prescribers by overall level of satisfaction with Levosert in patients who use it for three or more years, by indication

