# of total patients / month	

- **Q2.** Approximately, how many of your patients are **currently using** one of the following types of contraception by indication?
 - ✓ Oral/pill
 - ✓ Intrauterine device (IUD)
 - ✓ Intrauterine system (IUS)
 - ✓ Hormonal ring
 - ✓ Implant
 - ✓ Injection

	Contraception only	Heavy menstrual bleeding (with and without intended contraception)
# of patients currently using any of the above treatment types	#	#

Q3. Considering **all your patients by indication,** approximately what percentage are currently using the different types of contraception listed below?

	Contraception only	Heavy menstrual bleeding (with and without intended contraception)
Oral/pill	%	%
Intrauterine device (IUD)	%	%
Intrauterine system (IUS)	%	%
Hormonal ring	%	%
Implant	%	%
Injection	%	%
Total	100%	100%

Q4. Considering all your patients currently using intrauterine systems (IUSs) by indication, approximately what percentage are using Levosert (levonorgestrel)?

	Contraception only	Heavy menstrual bleeding (with and without intended contraception)
Proportion of patients currently using IUSs who receive Levosert	%	%

Q5. Considering **all** your patients ever having used and/or currently using **Levosert (levonorgestrel)**, what is the age distribution at the time of prescription, by indication?

	Contraception only	Heavy menstrual bleeding (with and without intended contraception)
16-24 years of age	%	%
25-34 years of age	%	%
35-44 years of age	%	%
45-54 years of age	%	%
55+ years of age	%	%
Total	100%	100%

Q6. When using **Levosert (levonorgestrel)** for **heavy menstrual bleeding (with and without intended contraception)**, what is the average time from insertion to achieving treatment effectiveness (defined as significant reduction in menstrual blood loss)?

1	Less than one month	
2	One to less than two months	
3	Two to less than three months	
4	Three to less than four months	
5	Four months or more	

Q7. In your experience, approximately what percentage of patients using **Levosert (levonorgestrel)** for the following indications need to get it **removed (with or without replacement)** by the end of each year (cumulatively since insertion)?

Please note your responses must be cumulative over time (since insertion).

	Contraception only	Heavy menstrual bleeding (with and without intended contraception)
By the end of Year 1	%	%
By the end of Year 2	%	%
By the end of Year 3	%	%
By the end of Year 4	%	%
By the end of Year 5	%	%

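### Two secondary endpoints are worded as distributions of patients, but items 10 and 11 of section 10.3 list only summaries of per-prescriber percentages, and no listed analysis names the Q2 patient counts

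*Protocol*

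**What the plan says.** In the Protocol synopsis (Sample Size and Statistical Analysis), the secondary endpoints include "distribution of patients by type of contraception, distribution of patients using IUSs who are receiving Levosert". The unit in both is the patient.

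Section 10.3 implements them in two items:

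- Item 10: "Descriptive statistics on percentage of Prescribers' patients by type of contraception, by indication".
- Item 11: "Descriptive statistics on percentage of Prescribers' patients using IUSs who are receiving Levosert, by indication".

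The same section says what such statistics are: "Continuous variables will be summarized using the number of observations (n), mean, standard deviation (SD), median, minimum, and maximum", with IQR and 95% CI as appropriate.

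The inputs are in Appendix 3. Q2 asks each prescriber for the number "of patients currently using any of the above treatment types", separately for contraception only and for HMB. Q3 asks "approximately what percentage are currently using the different types of contraception listed below", with each indication column totalling 100%. Q4 asks for one percentage per indication, the share of current IUS users who are on Levosert.

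Among the listed analyses that use volumes, item 7 covers IUS prescriptions, item 8 Levosert prescriptions and removals, and item 9 the patients managed in a typical month. No item names Q2, and section 10 mentions no weighting.

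**The concern.** A mean or median of prescriber percentages gives a respondent with 10 users the same influence as one with 500. It answers what the typical prescriber's mix looks like. A distribution of patients answers what share of these prescribers' patients use each method, or use Levosert among IUS users. The two answers differ whenever prescribers with large caseloads choose differently from those with small ones. Reporting by country does not cure this, because prescribers also differ within a country.

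The study report goes to a competent authority and publication is foreseen (section 12.6). A reader who sees a percentage under an endpoint named as a distribution of patients will take it as a percentage of patients. The count needed to produce that figure is already collected.

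**Working it through.** **Plan's own figure.** The Protocol states no expected value, precision or sample size for the method mix or the Levosert share, so there is no figure to reproduce for these endpoints. What can be checked is whether its own feasibility data show unequal volume per prescriber.

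**Volume per prescriber (Appendix 1, Table 3).** Quota x removals / practising OB-GYNs:

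- Czech Republic: 80 x 7,400/2,600 = 227.7
- Poland: 150 x 16,900/5,900 = 429.7
- Serbia: 100 x 1,100/1,600 = 68.8
- Slovakia: 50 x 2,100/1,100 = 95.5
- Total: 821.6, against 821 stated, which reproduces.

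With one vote per prescriber, Serbia carries 100/380 = 26.3% of an all-country summary. By expected removals it carries 68.75/821.6 = 8.4%. Poland goes from 150/380 = 39.5% to 429.7/821.6 = 52.3%. Removals are only a proxy for the current-user counts in Q2, but they show that the Protocol itself expects unequal volumes.

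**The two estimators.** For prescriber j, let x_j be the reported share and w_j the number of patients it refers to.

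- Item 10: x = Q3 for the method, w = Q2. The six methods in Q3 total 100% and are the six counted in Q2, so Q2 is the matching base.
- Item 11: x = Q4, w = Q2 x Q3-IUS (the number of IUS users). Q2 alone would be the wrong weight.

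Prescriber mean = sum(x_j)/J. Patient share = sum(w_j x_j)/sum(w_j). Their difference is exactly

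patient share - prescriber mean = Cov(w, x)/mean(w) = r x SD(x) x CV(w),

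where r is the correlation between caseload and share.

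**Size under assumed inputs.** SD, CV and r are all assumptions; the Protocol gives none of them.

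- SD 25 points, CV 1.0: r = 0.1, 0.2, 0.3, 0.5 gives 2.5, 5.0, 7.5, 12.5 points.
- Low end, SD 15, CV 0.75, r = 0.1: 0.1 x 15 x 0.75 = 1.1 points.
- High end, SD 30, CV 1.5, r = 0.5: 0.5 x 30 x 1.5 = 22.5 points.
- r = 0 gives 0. Negative r gives the same sizes with the opposite sign.

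**Two-prescriber illustration (assumed and deliberately extreme).** One has 10 IUS users with 90% on Levosert, the other 200 with 20%. Prescriber mean: (90 + 20)/2 = 55%. Patient share: (9 + 40)/210 = 23.3%. The identity agrees: r = -1, SD = 35, CV = 95/105 = 0.905, so the gap is -31.7 points.

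**Price in precision.** With unequal weights, effective n is about n/(1 + CV²). At CV 1.0 the 380 respondents act like 190 and Slovakia's 50 like 25. At CV 1.5 the divisor is 3.25, giving about 117 and 15.

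**The case against.** The strongest reply is that equal weighting is never stated. Section 10 calls itself an overview, section 10.3 allows statistics as appropriate, and a statistical analysis plan not shown here could specify weights. Q2 stands directly before Q3, covers the same methods and is split by the same indications, so it may well be meant as the base. This stands to the following extent: equal weighting is an inference from the listed statistics and the absence of any weight. It does not dispose of the point, because section 10.3 already fixes the summaries for these two items, and followed as written they do not yield the endpoint as worded.

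Second, section 6.2 sets out to characterise prescribing practices amongst OB-GYNs. Prescriber-level summaries serve that objective and are not an error. The fault lies in presenting them as distributions of patients.

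Third, weighting has a real cost. Q2 is an approximate, recalled count with no range check shown in the questionnaire, and the weight for item 11 is a product of two recalled figures. A few large or mistaken counts could dominate.

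Three stronger readings are tempting and are not supported. A reader might infer that the sponsor has decided to ignore Q2; the Protocol does not map questions to analysis items, so one can say only that no item names it. A reader might infer that prescribers with no users in a column must still fill Q3 to 100% and enter the average in full; the document gives no routing or analysis rule for Q2 = 0. And a reader might take the reported percentages to be badly biased; without Q2 to Q4 data, neither the size nor the direction can be established.

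**Conclusion.** The mismatch of unit holds on the plain reading: patient-level endpoints, prescriber-level summaries, and a collected denominator that no listed analysis names. The planned figures equal the patient distribution only if share and caseload are uncorrelated. The gap is about 1 to 22 points in either direction for SD 15 to 30 points, CV 0.75 to 1.5 and an absolute correlation of 0.1 to 0.5, all assumed, and zero if they are unrelated.

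The consequence is limited. The study tests no hypothesis, neither quantity enters the usage-duration formula in section 10.1, and respondents are a convenience sample screened for prescribing and removing Levosert in HMB. Even pooled figures would describe only the patients of these prescribers. The point is worth correcting because the correction needs no new data, not because a main conclusion depends on it.

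**What to change.** In section 10.3, items 10 and 11:

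- Keep the prescriber-level summaries and label them as describing prescribing practice.
- Add beside them, by country and indication, the pooled patient estimates: sum(Q2 x Q3)/sum(Q2) for each method, and sum(Q2 x Q3-IUS x Q4)/sum(Q2 x Q3-IUS) for the Levosert share of IUS users. Take 95% CIs from a bootstrap that resamples prescribers.
- State the unit, prescriber or patient, with every figure.
- Check the influence of extreme Q2 values, for example by repeating the pooled estimates without the largest counts.
- If the pooled estimates are not to be reported, reword the two synopsis endpoints as prescriber-level percentages.

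The cost is a few sentences and a little code; the questionnaire does not change. The downside is wider intervals and sensitivity to recalled counts, which is why the pooled figures belong beside the prescriber summaries and not in their place.

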4 LIST OF ABBREVIATIONS

Abbreviation	Definition
DCP	Decentralised Procedure
DUS	Drug Utilization Study
HCP	Healthcare Provider
HMB	Heavy Menstrual Bleeding
ICF	Informed Consent Form
ICH	International Council for Harmonisation
IUS	Intrauterine System
LNG	Levonorgestrel
OB-GYN	Obstetrician - Gynaecologist

5 BACKGROUND AND RATIONALE

5.1 Background

Levosert®is a levonorgestrel (LNG)-releasing intrauterine system (IUS) containing 52 mg of levonorgestrel. When inserted into the uterus, it slowly releases this hormone to be absorbed by the user. The initial release of levonorgestrel is approximately 20 micrograms per day. This rate decreases progressively to approximately 8.6 micrograms/day after 6 years. The average in vivo release rate of LNG is approximately 14.3 micrograms/day over a period of 6 years.

In Europe, Levosert is indicated for use in 1) contraception and 2) heavy menstrual bleeding, hereafter referred to as menorrhagia or HMB.

- 1) Contraception. Levosert prevents pregnancy by thinning the lining of the uterus, by making the normal mucus in the opening of the uterus thicker, so that the sperm cannot get through to fertilise the egg and by preventing ovulation in some women.
- 2) Treatment of menorrhagia. The hormone in Levosert acts by thinning the lining of the uterus, so that there is less bleeding every month.

Levosert was first authorised in Europe via Decentralised Procedure (DCP; licence number UK/H/3030/001/DC) on 28 Dec 2012 for the treatment of menorrhagia for three years. Countries targeted for the proposed study (Czech Republic, Poland, Serbia, and Slovakia) authorized Levosert for the treatment of menorrhagia in a separate DCP (HU/H/0580/001/DC) in 2013. The applications were based on a therapeutic equivalence study conducted with Levosert and Mirena®. On 16 Oct 2014, the second indication 'contraception' was approved with new supportive data from the ongoing pivotal Phase 3 study M360-L102. Since then and based on the results of the same Phase 3 study, the duration of use of Levosert for use in contraception extended to 5 years, then to 6 years in all European countries where the product is marketed. However, the ongoing Study M360-L102 was designed to evaluate contraceptive efficacy only (not menorrhagia), and thus, there is need for further evidence regarding usage for the menorrhagia indication to support its use up to the recommended duration determined for the contraception indication.

5.2 Rationale

In the context of a lack of data to support extension of recommended duration of use for menorrhagia indication, Gedeon Richter has committed to the Danish Medicines Agency to conduct a drug utilisation study (DUS) concerning the real-world usability of Levosert 20 microgram/24 hours Intrauterine Delivery System in the HMB indication.

13-02-2023 This document is confidential.

6 OBJECTIVES

This descriptive study aims to generate insights into the real-world prescribing practices and usability/utilization of Levosert, including duration of use, for the treatment of HMB (with and without intended contraception) within the selected countries.

6.1 Primary Objective

The primary objective is to describe the duration of Levosert utilization for the indications of contraception and HMB (with and without intended contraception) amongst prescribing OB-GYNs in the selected countries.

